#### 6.1.2 Part 2: Comparison of independent sample rates between the two groups

Comparison of the independent sample rates of the two groups: the infection rate of at least one pathogen in the whole population is about 0.01%, and the infection rate of patients who visited our hospital for infertility is about 0.46%, and this data was brought into SPSS software: Confidence Intervals for the Difference Between Two Proportions,  $n=114$  cases, so 114 cases were included in the experimental group and the control group each

#### 6.2 Grouping method

Case group were patients with clinical diagnosis of infertility: sexually active, uncontraceptive and infertile for 2 years

The control group was those with spontaneous pregnancy: those with spontaneous pregnancy at the follow-up visit 3 months after consultation

### 7. Interventions

This study did not involve an intervention

### 8. Research steps

#### **8.1 Part I. Development of a rapid detection method based on MALDI-TOF MS for simultaneous detection of multiple pathogens and CST in the lower genital tract and evaluation of diagnostic efficacy**

8.1.1 Find the relatively conserved regions of virulence factor sequences of each pathogen according to the database, intercept the specific sequences from the conserved regions of each pathogen to design multiplex PCR amplification primers and single base extension (SBE) primers for each strain to construct MALDI-TOF MS assays.

8.1.2 Purchase standard pathogen strains, culture standard concentrations (i.e., high concentrations) of standard pathogens using the culture method to identify standard pathogens and their activities

8.1.3 Formulation of single, mixed and negative control standards with standard pathogens.

8.1.4 Gold standard: The actual pathogen type added to the standard is the gold standard.

8.1.5 Detection of standards at gradient dilution concentrations by incubation method and MALDI-TOF MS, respectively.

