The vast majority of patients with lower genital tract pathogens are only transiently infected and can be cleared by their own or pharmacological treatment, while only a minority of patients have serious adverse outcomes, suggesting that other factors influence the pathogenic evolution of these pathogens. Previous studies have shown that the type and abundance of long-term parasitic flora in the human cavity are closely related to important aspects of disease development such as immune regulation, inflammatory response, cytogenetic mutation, angiogenesis, and tissue remodeling. . Therefore, in recent years, microecology has received a lot of attention from many fields such as immunity and metabolism. Since the discovery of *Lactobacillus vaginalis* by Albert Doderlein in 1982, a number of studies have been conducted to demonstrate that a decrease in the absence of *Lactobacillus vaginalis* is a major cause of inflammatory vaginal diseases such as mycobacteria and bacterial vaginitis. However, because early studies on genital tract pathogens were mainly performed by microbiological microscopy, staining, and culture, it was not possible to subtype *Lactobacillus*, and the correlation between lower genital tract CST and obstetrical and gynecological diseases has only recently been emphasized. Recently, many scholars have studied the relationship between vaginal CST and obstetric and gynecological diseases, and such studies have suggested that abnormal CST in the lower genital tract can lead to pelvic inflammatory disease infertility and adverse pregnancy outcomes. However, does abnormal CST promote gonorrhea? However, it is unclear whether CST abnormalities promote infection and persistence of infertility-causing pathogens such as *Neisseria gonorrhoeae*, *Mycoplasma*

urealyticum and Chlamydia trachomatis.

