## **6. estimation of sample size and grouping method**

### 6.1 Estimation of sample size

#### 6.1.1 Part I: Comparison of sensitivity of dose information between the two groups

Single and mixed standard bacterial solutions and blank controls were 11 in total, so the chance of the appearance of four microorganisms in various standard strain solutions was 0.18, and different studies showed that the culture sensitivity of gonococci, lactobacilli, mycoplasma, and chlamydia was 40-60% and specificity 95-98%; time-of-flight mass spectrometry detection was >99% in different studies, and the parameters were brought into

PASS according to  $\alpha=0.1$  Software calculation path: Tests for Two Independent Sensitivities,  $N=44-72$ , taking the least integer multiple of 11 for  $>72$ , i.e., 77 cases in each group

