8.1.6 Performing diagnostic effectiveness analysis

## **8.2 Part II Assessment of the association between lower genital tract pathogen infection, CST and infertility using newly developed assays**

8.2.1 Select infertile women of childbearing age who meet the criteria for nadir to sign informed consent and be enrolled in the study.

8.2.2 Completion of an information collection form to obtain information on **confounding factors that** may affect this study (age, weight, height, ethnicity, ancestry, place of long residence, number of pregnancies and births, time of last menstruation and menstrual cycle, duration of infertility, relevant diagnoses leading to infertility, etc.), which is collected daily by the information management specialist and kept.

8.2.3 Sample collection: take cervical canal and vaginal secretions during routine gynecological examination and routine leucorrhea examination secretions during routine consultation. ④ Place the swab head in sterile storage solution and tighten the cap ⑤ Label the bottle with patient information ⑥ Store in 4°C refrigerator.

8.2.4 Isolation and extraction of pathogen DNA.

8.2.5 Detection of microorganisms in the lower genital tract by a constructed MALDI-TOF MS assay.

8.2.5 Uniform disposal of remaining specimens in accordance with medical waste after sample testing is completed.

8.2.6 Statistical analysis to assess the correlation between various pathogenic infections and CST status and infertility separately

[figure not shown]
8.2.7 Statistical analysis to assess differences in CST status between infected and uninfected individuals with various pathogens

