10.2 MALDI-TOF MS test results were recorded as: microbial type, positive, negative

## 11. Security evaluation

This study involves only 1 vaginal and cervical secretion collection, which is consistent with HPV sampling during cervical screening in routine clinical testing and does not cause additional collection points or additional consultation costs, and is safe. It may cause pain and a little bleeding to the patient, neither of which will have any impact on the patient's health. Inform the patient before the operation to avoid causing panic. If the patient has intercourse immediately after the test or performs inappropriate transvaginal operations that may lead to infection, the patient is advised to avoid intercourse, sitz baths and other transvaginal operations without professional medical guidance for 3 days after sampling.

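### As the readable text stands, the plan gives no valid route from the recorded assay result to the CST variable used in objective 2, 8.2.6 and 8.2.7

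*Combined protocol and SAP*

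**What the plan says.** CST appears in the aims and in the analyses:

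- Section 3 names CST in both objectives, and the heading of 8.1 promises "simultaneous detection of multiple pathogens and CST in the lower genital tract and evaluation of diagnostic efficacy".
- 8.2.6 plans "Statistical analysis to assess the correlation between various pathogenic infections and CST status and infertility separately". 8.2.7 compares CST between women with and without each infection.

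The laboratory steps are written around pathogens:

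- 8.1.1, target choice: "Find the relatively conserved regions of virulence factor sequences of each pathogen according to the database". Primers for each strain are then designed from these regions.
- 8.1.3, standards: "Formulation of single, mixed and negative control standards with standard pathogens".
- 8.1.4, reference: "The actual pathogen type added to the standard is the gold standard".
- 8.2.4, extraction in Part II: pathogen DNA.

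The sample-size text in 6.1.1 nevertheless includes a non-pathogen, since it states that "the culture sensitivity of gonococci, lactobacilli, mycoplasma, and chlamydia was 40-60" per cent.

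The result kept for each woman is set in 10.2: "MALDI-TOF MS test results were recorded as: microbial type, positive, negative". The main indicator in the Program Summary is shorter still, a negative or positive result.

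The background describes CST as a property of the colonising bacteria (1.1). It also says that "the type and abundance of long-term parasitic flora in the human cavity are closely related to important aspects of disease development", faults older methods for not being able to subtype Lactobacillus, and reports that CST is now obtained by 16S rRNA or metagenomic sequencing (1.2).

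**The concern.** A community type describes the resident flora. The only stated rule for choosing targets looks for virulence factors in pathogens, and the only stated rule for recording keeps a call for each organism without its amount. Nothing in the readable text then turns those calls into a CST category.

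Two things are at stake. First, the CST half of objective 2 and the whole of 8.2.7 may turn out not to be analysable. Secondly, a pattern of detected organisms may be labelled CST after the event. In that case the definition could be chosen with the case and control results in view, and the conclusion would answer a different question from the one posed.

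**Working it through.** The plan states no figure for this point, so the check follows CST from aim to analysis.

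| Step | Where | What is specified for CST |
|---|---|---|
| Aim | 3; heading of 8.1 | CST named alongside pathogens |
| Targets | 8.1.1 | Virulence-factor regions of pathogens; no Lactobacillus species or other flora named |
| Standards and reference | 8.1.2-8.1.4 | Pathogen strains, pathogen standards, pathogen type added; no CST reference |
| Extraction | 8.2.4 | Pathogen DNA |
| Detection | 8.2.5 | Microorganisms in general; panel not listed |
| Recorded result | 10.2; Program Summary | Organism type with a positive or negative call; no abundance, no CST category |
| Analysis | 8.2.6, 8.2.7, 12 | CST used as a variable; tests listed, no categories or assignment rule |

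The chain therefore breaks at two specified steps, targets and recorded result, and is silent on assignment.

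**Targets.** 6.1.1 implies that lactobacilli are in the standard solutions, while 8.1.1-8.1.4 taken literally give them no target. The count of solutions does not settle what the panel is. Section 6.1.1 gives 11 solutions and a chance of 0.18 for each microorganism, and 2/11 = 0.18 reproduces that figure. Several schemes can be set against it:

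- four single strains + six pairs + one blank = 11, each organism in 1 + 3 = 4 solutions, 4/11 = 0.36, which does not match;
- nine single strains + one mixture of all + one blank = 11, each in 1 + 1 = 2, 2/11 = 0.18, which matches;
- four single strains + one mixture of all + six blanks = 11, each in 1 + 1 = 2, 2/11 = 0.18, which also matches.

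So 0.18 fits a panel of four strains or a wider one, and the documents do not list the strains.

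**Recorded result.** Assume that a community type reflects which organism dominates. This is general field knowledge; the documents do not say it. Take k flora organisms, all detected in a woman. Any of the k could dominate, so k states map to one record, all positive. For k = 2, two women with opposite proportions have the same record and cannot be told apart. Knowing the organism types does not help, because the types are the same.

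**Without that assumption.** The gap remains. No CST categories and no rule are stated, and abundance, which section 1.2 calls important, is not kept.

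**Size.** The CST part of 8.2.6 and all of 8.2.7 are affected, across 114 + 114 = 228 women. The effect on an estimate cannot be calculated, because the variable is not defined.

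**The case against.** The strongest reply is that the wording is loose and the intended panel is wider than 8.1.1 suggests. Lactobacilli appear in 6.1.1, 8.1.1 designs primers for each strain, 8.2.5 speaks of microorganisms, and 10.2 keeps organism type as well as the call. If several Lactobacillus species are on the panel, some grouping by presence or absence is possible. This stands. It means that 8.1.1-8.1.4 and 6.1.1 must be reconciled, and it rules out saying that lactobacilli are excluded. It does not supply abundance, categories or an assignment rule.

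Four stronger readings are tempting, and the documents do not support them:

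- *CST can never be derived from these data.* The flow charts in section 9 and figures near 8.2.6 and in 8.3 are not available here and might show the panel or the CST step. The point is limited to the readable text.
- *Lactobacilli give a single call, so at most two categories exist.* The genus label in 6.1.1 serves to quote culture sensitivity. Mycoplasma is also listed there once, yet 10.1 records two mycoplasma species separately.
- *Disposal of DNA makes the loss irreversible.* Under 8.3, DNA is kept at -80°C until it has been tested and the results analysed, so material is still held while CST is being analysed.
- *The sentence on type and abundance defines CST.* It concerns resident flora and disease in general. It supports the relevance of abundance, but it is not a definition.

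It is also fair to object that no section says the instrument gives a usable quantitative signal for each target, or that such a signal tracks abundance after multiplex PCR. This stands, and the fix is made conditional on it.

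**Conclusion.** The point holds in a limited form. On the readable text, the stated target rule and the stated recording rule do not lead to a CST variable, and nothing else in the plan bridges the gap. This goes beyond missing detail: followed literally, the two rules leave the CST analyses either undoable or resting on a presence pattern.

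The conclusion rests on the readable text being complete on this matter. The argument about identical records rests, in addition, on the dominance assumption; the absence of categories, rule and abundance does not. The change should be made before Part II data are analysed. The analyses of pathogen infection and infertility are not touched by this point.

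**What to change.** 1. **Targets.** Reconcile 8.1.1-8.1.4 with 6.1.1 and list the full panel. The target rule should cover the Lactobacillus species and the other flora that define the CSTs to be reported, with species-specific conserved sequences where an organism has no virulence factor.
2. **Record and rule.** In 10.2, keep the signal for each target as well as the call. State the CST categories and the rule that assigns them, fixed before case and control results are seen. Before relying on the signal, the sponsor must confirm that the instrument gives it and, from the Part I dilution series (8.1.5), that it tracks abundance.
3. **Fallback.** If this is not done, restate the CST part of objective 2, 8.2.6 and 8.2.7 as analyses of which organisms are detected, and draw conclusions on that only.

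Cost: items 1 and 2 need some extra primers, strains and standards in an assay still being designed. They may change the scheme of 11 solutions, and with it the 77 per group in 6.1.1, which was chosen as a multiple of 11. The fallback is a change of wording; its price is a narrower claim.

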	
8) Have the habit of smoking and drinking
 
Control group:
 
 
1) Pregnancy by various assisted reproductive means
 
2) Patients with malignant tumors
 
3) Patients with autoimmune diseases
 
4) Patients with severe heart, kidney and other basic diseases
 
5) Patients who consumed antibiotics 3 days before the examination
 
6) Have the habit of smoking and drinking
 

Exclusion Criteria
	
All samples tested in Part I were acquired standards with no inclusion criteria; Part II:
 
Case group:
 
 
1) Infertility due to malformation of reproductive tract
 
2) Infertility caused by endocrine factors such as polycystic ovary syndrome, premature ovarian failure and severe hyperthyroidism
 
3) Infertility due to male factors
 
4) Patients with malignant tumors
 
5) Patients with autoimmune diseases
 
6) Patients with severe heart, kidney and other basic diseases
 
7) Patients who consumed antibiotics 3 days before the examination
 
8) Have the habit of smoking and drinking
 
 
Control group:
 
 
1) Pregnancy by various assisted reproductive means
 
2) Patients with malignant tumors
 
3) Patients with autoimmune diseases
 
4) Patients with severe heart, kidney and other basic diseases
 
5) Patients who consumed antibiotics 3 days before the examination
 
6) Have the habit of smoking and drinking
 

Ending evaluation
	
Main indicators: microbiological test results, are recorded as negative, positive

indicators	
Safety evaluation indicators	Pain indicators: pain score; bleeding indicators: bleeding volume assessment (blood staining area method), blood routine; cervical and vaginal infection: white belt routine

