Currently, although inflammatory vaginal diseases such as mycosis fungoides, bacterial vaginosis, and trichomoniasis can be detected rapidly (30-60 minutes) by simultaneous routine leukocyte or vaginal microecological evaluation. However, in order to assess the infection status of the lower genital tract, sampling, culture and testing of *Neisseria gonorrhoeae*, mycoplasma and chlamydia need to be performed separately, which takes a long time (ranging from 2-5 days) and increases the patient's pain and may lead to an increase in the false-negative rate of the later specimens due to repeated sampling, and CST analysis is costly and time-consuming due to the use of 16SrRNA and high-throughput sequencing. Currently, CST analysis is only used in scientific research and lacks practical significance for clinical diagnosis and treatment of patients.

The emerging Matrix-Assisted Laser Desorption/Ionization Time of Flight Mass Spectrometry (MALDI-TOF MS) detection system can detect multiple pathogenic microorganisms and subtypes simultaneously than traditional detection techniques such as fluorescent PCR technology, with high detection stability and accuracy, and lower cost and faster analysis than second-generation sequencing, and has been gradually used in recent years. in clinical testing The project team has previously used MALDI to detect a variety of pathogenic microorganisms. The project team has previously established a cervical fluid-based cell PAX1 methylation detection platform using MALDI-TOF MS (**Patent No. CN202010753067.8., paper submitted**), and has extensive experience in the development of MALDI-TOF MS platform for clinical testing. This study will use the MALDI-TOF MS platform to establish a combined detection system for common pathogens in the lower genital tract and CST to fill this technical gap and address the practical needs of clinicians.

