### **4. Study design**

The first part of this study is a diagnostic test using using a standard pathogenic strain; the second part is a prospective case-control study

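### Part I lists no human DNA, swab matrix or non-target vaginal organism, so its sensitivity and specificity cannot be carried over to the Part II swabs without further evidence

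*Combined protocol and SAP*

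**What the plan says.** The Program Summary states "All samples tested in Part I were acquired standards with no inclusion criteria", and section 4 describes Part I as a diagnostic test on a standard strain. Section 6.1.1 gives the panel: "Single and mixed standard bacterial solutions and blank controls were 11 in total". It adds that "the chance of the appearance of four microorganisms in various standard strain solutions was 0.18" and names gonococci, lactobacilli, mycoplasma and chlamydia. Section 8.1.3 describes the recipe as "Formulation of single, mixed and negative control standards with standard pathogens". Section 8.1.4 takes what was added to each solution as the reference standard, and section 8.1.5 tests the standards at graded dilutions by culture and by MALDI-TOF MS. Section 12, item c, plans sensitivity, specificity and both predictive values from this part.

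Part II uses different material. Section 8.2.3 says to "take cervical canal and vaginal secretions during routine gynecological examination", and the extracted DNA then goes through the new assay. The Part II methods in section 12 are chi-square, rank sum, stratified and logistic analyses. Section 10.1 records clinical reports for mycoplasma, chlamydia and gonococcus, and section 10.2 records the MALDI-TOF MS result. No analysis compares the two.

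**The concern.** A specificity estimate describes only the negatives that were tested. As described, the negatives for each organism are blanks and solutions of other standard strains. A swab also carries human DNA, mucus and whatever else lives in the tract. The protocol's own background discusses such conditions, noting that "bacterial vaginosis, and trichomoniasis can be detected rapidly". If a primer cross-reacts with an organism absent from the panel, Part I specificity is unaffected and Part II collects false positives. If secretions inhibit amplification, Part I sensitivity is unaffected and Part II loses true positives.

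Two Part II results depend on this. False positives dilute the infertility comparison in section 8.2.6 if they are equally frequent in both groups, and bias it in either direction if they are not. In section 8.2.7, pathogen status and CST come from the same assay, so cross-reaction that varies with flora could itself produce an association between CST and pathogen.

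**Working it through.** **1. The plan's own figure.** Inputs from section 6.1.1: culture sensitivity 0.40 to 0.60, MALDI-TOF MS 0.99, alpha 0.1, share of solutions containing an organism 0.18. Power and sidedness are not given; I assume 80% and two-sided. With p̄ the mean of the two sensitivities,

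n = [1.645·√(2p̄(1−p̄)) + 0.842·√(p₁(1−p₁)+p₂(1−p₂))]² / (p₂−p₁)².

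- 0.60 against 0.99: n = 12.16, so 13 positives; 13/0.18 = 72.2. This matches the printed upper end of 72, and the next multiple of 11 is 77.
- 0.40 against 0.99: n = 6.39, so 7 positives; 7/0.18 = 38.9. The printed lower end of 44 does not reproduce under these settings, but it does not affect the 77.

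**2. Negatives per organism.** Reading 0.18 as 2/11: positives 77 × 2/11 = 14; negatives 77 × 9/11 = 63.

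The type of negative depends on a layout that is not written out:
- Nine singles, one mixture of all strains and one blank gives 2/11: 56 negatives from other strains and 7 from the blank.
- Exactly four organisms, each in two solutions, makes 8 placements. With at least one mixture, at most 7 solutions hold any organism. At least 4 of the 11 are then blanks, or at least 28 of the 63 negative tests.
- Four singles, six pairs and one blank also makes 11, but gives 4/11 = 0.36 rather than 0.18, with 49 negatives.

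**3. What clean negatives would show.** If all n are negative, the exact 95% lower bound is 0.025^(1/n), treating the runs as independent:
- n = 63: 94.3%
- n = 49: 92.7%

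Neither bound covers flora or human DNA, because no listed negative contains them.

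**4. Size in Part II (illustration).** Swab specificity is not in the documents; I assume 99% to 95%. False positives per organism among 114 uninfected women are 114 × (1 − Sp). The any-of-four column assumes four independent targets, 1 − Sp⁴.

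| Assumed Sp | Per organism | Any of four targets |
|---|---|---|
| 99% | 1.1 | 3.9% (4.5 women) |
| 98% | 2.3 | 7.8% (8.9 women) |
| 95% | 5.7 | 18.5% (21.1 women) |

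Expected infected women per group of 114, from the any-pathogen rates in section 6.1.2:
- As printed (0.46% and 0.01%): 114 × 0.0046 = 0.52 cases; 114 × 0.0001 = 0.01 controls.
- If meant as proportions (0.46 and 0.01): 114 × 0.46 = 52.4 cases; 114 × 0.01 = 1.14 controls.

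**5. Effect on the odds ratio.** Assume perfect sensitivity and the same specificity, for the any-pathogen call, in both groups. The observed rate is p + (1−p)(1−Sp).

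| Rates | True odds ratio | Sp 99% | Sp 95% |
|---|---|---|---|
| As printed | 46 | 1.4 | 1.1 |
| As proportions | 84 | 43 | 15 |

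For example, as proportions at 95%: cases 0.46 + 0.54 × 0.05 = 0.487; controls 0.01 + 0.99 × 0.05 = 0.0595; odds ratio (0.487/0.513)/(0.0595/0.9405) = 15.

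**The case against.** Testing known standards first is a legitimate analytical stage. Section 8.1.1 selects sequences specific to each pathogen and adds a single-base extension step, and poor extraction is an exit criterion in section 5.3. These bear on cross-reaction and inhibition, but they are design intentions and quality filters rather than tests against non-target material.

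Several stronger readings are tempting, and the documents do not support them:
- A reader might infer that Part I specificity is the only evidence that a Part II positive is real. Section 10.1 records clinical reports that may provide a comparator on swabs. What is missing is the analysis, and a statement that the reports cover the Part II women.
- A reader might infer that Part I has no chance at all of meeting a non-target organism. The panel is not fully listed. The nine-single layout fits 0.18 and leaves up to five strains unnamed, the diluent is not described, and the Part I flow chart is not shown in the copy reviewed. The supportable statement is that none is listed.
- A reader might infer that Part I specificity will look near perfect. That cannot be computed: cross-reaction between targets or carry-over could still appear.
- A reader might infer that the protocol calls fungal disease, bacterial vaginosis and trichomoniasis common. Section 1.1 says only that they can be detected quickly; it says common of lower genital tract infections in general.

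Two practical objections stand and shape the fix. Live background organisms would disturb the culture comparator and the 40–60% sensitivity behind the sample size. Leftover target-negative secretions are a poor source of background, because lactobacilli are themselves a target.

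**Conclusion.** The point holds in this form: as described, Part I cannot detect cross-reaction with non-target flora or inhibition by secretions, and its sensitivity and specificity are not shown to carry over to the Part II swabs. Part I remains valid as analytical work on pure standards.

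The 63 negatives and the 94.3% bound rest on reading 0.18 as 2/11 and on all negatives being clean. The 1.1 to 5.7 false positives rest on an assumed swab specificity. They outnumber the expected true positives at the printed rates. If the rates were proportions, they are small beside the 52 infected cases but equal or exceed the 1.1 infected controls. The change is a cheap improvement worth making before Part I runs.

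**What to change.** 1. In section 8.1.3, list the 11 solutions, their strains and the diluent.
2. Keep 11 solutions and 77 tests. Make most negative-control runs background-only (human DNA plus DNA of non-target vaginal organisms) and keep at least one pure blank run.
3. Add the same background to the aliquots tested by MALDI-TOF MS and not to those cultured, so the culture comparator is unchanged.
4. Report specificity separately for blank, other-target and background-only negatives. In the nine-single layout with one blank run kept, there are 6 background-only runs, whose bound if clean is only 0.025^(1/6) = 54.1%. The 56 other-strain runs also carry the background, however, and 62 clean runs give 0.025^(1/62) = 94.2%.
5. If the section 10.1 reports are available for the Part II women, add a planned agreement analysis against the section 10.2 results. Report it as positive and negative agreement, because the plan itself puts culture sensitivity at 40–60%. This is also the only step that uses real secretions; a DNA background does not reproduce inhibition by mucus.

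Cost: a few extra strains or DNA preparations, a revised recipe and one added analysis. MALDI-TOF MS sensitivity and specificity may come out less favourable. A pooled background would not identify which organism cross-reacts, so any signal would need follow-up runs.
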